### **5.3. Lifestyle Considerations**

No restrictions to diet or lifestyle are required.

### **5.4. Screen Failures**

Screen failures are defined as participants who consent to participate in the clinical study but do not subsequently receive study treatment.

Tests with results that fail eligibility requirements may be repeated once during screening if the investigator believes the result to be in error. Additionally, a participant who fails screening may repeat the screening process 1 time if the investigator believes there has been a change in eligibility status. Participants who rescreen must reconsent and be assigned a new participant number.

## **5.5. Replacement of Participants**

Participants who do not experience a DLT and do not receive at least 3 doses of tafasitamab and 21 days of treatment with parsaclisib 20 mg QD will be replaced to ensure that there are 10 evaluable participants within each disease-specific cohort.

## **5.6. Data Safety Monitoring Board**

An iDSMB will review data once the 10th DLT-evaluable participant from any cohort completes the DLT evaluation period (C1D28 or experiences a DLT). Reviews will be repeated every 4 months thereafter. The occurrence of DLTs in 2 or more of the first 10 DLT-evaluable participants will also trigger an iDSMB review. Details regarding the composition and responsibilities of the iDSMB are provided in the charter.

## 6. STUDY TREATMENT

### 6.1. Study Treatments Administered

Table 6 presents the study treatment information.

**Table 6: Study Treatment Information**

	Study Drug 1	Study Drug 2
Study drug:	Tafasitamab	Parsaclisib
Mechanism of action:		
Dosage formulation:		
Unit dose strength(s)/ dosage level(s):		
Administration instructions:		
Packaging and labeling:		
Storage:		
Status of treatment in participating countries:		

### 6.2. Preparation, Handling, and Accountability

The investigator or designee must confirm appropriate temperature conditions have been maintained during transit for all study treatments received and any discrepancies are reported and resolved before use.

Only participants enrolled in the study may receive study treatment, and only authorized site staff may supply or administer study treatment. All study treatment must be stored in a secure,

environmentally controlled, and monitored (manual or automated) area in accordance with the labeled storage conditions with access limited to the investigator or authorized site staff.

The investigator (or designee) is responsible for study treatment accountability, reconciliation, and record maintenance (ie, receipt, reconciliation, and final disposition records). Inventory and accountability records must be maintained and readily available for inspection by the study monitor and are open to inspection at any time by any applicable regulatory authorities. The investigator or designee must maintain records that document the following:

- Delivery of study drugs to the study site.
- Inventory of study drugs at the site.
- Participant use of the study drugs, including pill and vial counts from each supply dispensed.
- Lot numbers and/or vial numbers of study drug.
- Return of study drug to the investigator or designee by participants

The investigational product must be used only in accordance with the Protocol. The investigator will also maintain records adequately documenting that the participants were provided the specified study drug. These records should include dates, quantities, and any available batch or serial numbers or unique code numbers assigned to the investigational product and study participants.

[figure not shown]
Completed accountability records will be archived by the site. The investigator or designee will be expected to collect and retain all used, unused, and partially used containers of study drug until verified by the study monitor (unless otherwise agreed to by the sponsor). At the conclusion of the study, the investigator or designee will oversee shipment of any remaining study drug back to the sponsor or its designee for destruction according to institutional SOPs. If local procedures mandate on-site destruction of the investigational supply, the site should (where local procedures allow) maintain the investigational supply until the study monitor inspects the accountability records in order to evaluate compliance and accuracy of accountability by the investigative site. At sites where the study drug is destroyed before monitor inspection, the monitors rely on documentation of destruction per the site SOP.

### **6.2.1. Tafasitamab**

Tafasitamab will be dosed at 12 mg/kg based on actual body weight via IV infusion. Tafasitamab will be administered on Days 1, 8, 15, and 22 of Cycles 1 through 3 and then Days 1 and 15 of each 28-day cycle from Cycle 4 onward. Lyophilized powder must be reconstituted and diluted prior to infusion.

### **6.2.1.1. Reconstitution**

Reconstitution of tafasitamab should be performed as follows:

[figure not shown]

### **6.2.1.2. Dilution**

Dilution of tafasitamab should be performed as follows:

### **6.2.1.3. Administration**

### **6.2.2. Parsaclisib**

Participants will self-administer parsaclisib as an oral treatment. Parsaclisib will be administered as 20 mg QD for 8 weeks followed by 2.5 mg QD.

Parsaclisib should be taken at approximately the same time each day.

Administration of parsaclisib will be calendar-based. Delays or interruptions in study treatment will not affect the dosing schedule of parsaclisib; 20 mg QD will be administered only during the first 8 weeks (Days 1-56); all participants will switch to 2.5 mg QD on Day 57.

Treatment with parsaclisib will continue until a criterion is met for treatment discontinuation.

Parsaclisib will be administered in the study clinic on days when blood samples are collected for PK as indicated in Table 3 and Section [8.4](#).

See [Appendix F](#) for instructions to participants for handling parsaclisib.

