**Figure 1: Study Design Schema**

**Table 3: Schedule of Activities**

Visit Day (Range)	Screening	Treatment						EOT	Follow-up			Notes
		Cycles 1-3			Cycle 4 Onward				Safety	Disease	Survival	
		Days -28 to -1	Day 1 (± 1 d)	Day 8 (± 1 d)	Day 15 (± 1 d)	Day 22 (± 1 d)	Day 1 (± 1 d)	Day 15 (± 1 d)	EOT + 90 d	Post- Treatment	Last Visit + 12 Wk (± 7 d)	
Administrative procedures												
Informed consent	X											
Contact IRT	X	X				X		X	X			
Inclusion/exclusion criteria	X	X										Verify eligibility on C1D1.
General/disease medical history	X											
Prior/concomitant medications	X		X				X	X				
PJP prophylaxis			X									Required while receiving study treatment and for 2-6 months after the last dose of study treatment.
Dispense parsaclisib		X				X						
Administer parsaclisib		X	X	X	X	X	X					20 mg QD: Cycle 1, 2: Days 1-28.  2.5 mg QD: C3D1 onward Given on-site on PK assessment days.
IRR prophylaxis		X*	X*	X*	X	X	X					*Mandatory for first 3 doses.
Administer tafasitamab		X	X	X	X	X	X					12 mg/kg IV Cycles 1-3: Days 1, 8, 15, and 22 Cycle 4 onward: Days 1 and 15 only
Distribute reminder cards		X	X	X	X	X	X					
Assess treatment compliance			X	X	X	X	X	X				

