### **6.5. Dose-Limiting Toxicity and Determination of the Recommended Phase 2 Dose**

#### **6.5.1. Definition of a Dose-Limiting Toxicity**

Dose-limiting toxicity will be defined as the occurrence of any of the toxicities in [Table 7](#) up to and including Day 28 (Cycle 1/Day 28), except those with a clear alternative explanation. All DLTs will be assessed for severity by the investigator using CTCAE v5.0 criteria.

During the DLT evaluation period, participants who receive at least 3 of 4 doses of tafasitamab and 21 days of parsaclisib 20 mg QD or have a DLT will be considered evaluable for the dose confirmation period.

Dose reductions for individual participants may be made based on events observed at any time during the treatment period; however, for the purposes of opening each expansion cohort, decisions will be made based on events that are observed from the first day of study treatment administration through and including the final day of Cycle 1 (Cycle 1/Day 28).

An event clearly associated with the underlying disease, disease progression, a concomitant medication, or comorbidity will not be considered a DLT.

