**Table 8: Guidelines for Interruption and Restarting of Study Treatment**

Adverse Event	Value or Grade	Recommendation
Grade 3/4 neutropenia judged to be related to study drugs	ANC decreases to $< 1.0 \times 10^9/L$ for at least 7 days OR ANC decreases to $< 1.0 \times 10^9/L$ with an associated body temperature $\geq 38.5^{\circ}C$ ( $101.3^{\circ}F$ ) OR ANC decreases to $< 0.5 \times 10^9/L$	Interrupt tafasitamab and parsaclisib dosing. Follow CBC every 7 days. Growth factors (eg, G-CSF) and antimicrobial prophylaxis are to be used, as per local guidelines.
	ANC returns to $\geq 1.0 \times 10^9/L$	Provided all other criteria are fulfilled, resume dosing of tafasitamab and/or parsaclisib at the same dose. Monitor as clinically indicated.
Grade 2-4 thrombocytopenia judged to be related to study drugs	Platelet count decreases to $< 75 \times 10^9/L$	Interrupt tafasitamab and parsaclisib dosing. Follow CBC every 7 days.
	Platelet count decreases to $\geq 75 \times 10^9/L$	Provided all other criteria are fulfilled, resume dosing of tafasitamab and/or parsaclisib at the same dose. Monitor as clinically indicated.
Other clinically significant toxicities judged to be related to study drugs	Grade 3	Interrupt the administration of the study drug(s) to which the toxicity is judged to be related to up to 28 days until the toxicity has resolved to $\leq$ Grade 1.
	Toxicities resolve to $\leq$ Grade 1	Restart tafasitamab and parsaclisib at the same doses. If assessed as related to parsaclisib, restart at the next lower dose of parsaclisib (see Table 11). Monitor as clinically indicated.
	Recurrent Grade 3 after 2 dose reductions of parsaclisib	Discontinue tafasitamab and parsaclisib administration and follow-up per Protocol. Exceptions require approval of sponsor.
	Grade 4	Discontinue tafasitamab and parsaclisib administration and follow-up per Protocol. Exceptions require approval of sponsor.

CBC = complete blood count.

Note: If, based on medical judgment, the treating physician considers a laboratory parameter change or AE not to be a study drug-related toxicity, but to represent a natural fluctuation in or progression of the underlying disease, then it is at the physician's discretion and assessment of the individual risk/benefit ratio to determine whether the participant should be dosed. The decision and rationale behind the decision should be documented in the source data.

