**Table 11: Dose Levels for Parsaclisib**

	Dose, C1D1 to C2D28 (Day 1 to Day 56)	Dose, C3D1 to EOT (Day 57 to EOT)
Starting dose	20 mg QD	2.5 mg QD
First dose reduction	10 mg QD	1 mg QD
Second dose reduction	5 mg QD	Not applicable

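### The Day 57 switch to parsaclisib 2.5 mg QD has no exception for participants already dose-modified for toxicity, which conflicts with Table 12 and, if its rows are read across, with Table 11

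*Protocol*

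**What the plan says.** **The calendar rule.** Protocol Section 6.2.2 gives parsaclisib 20 mg QD on Days 1 to 56, after which "all participants will switch to 2.5 mg QD on Day 57". The same sentence opens by saying that "Delays or interruptions in study treatment will not affect the dosing schedule of parsaclisib". It names delays and interruptions but not dose reductions, and the section does not refer to the dose-modification rules in Section 6.6. The parsaclisib note in the Schedule of Activities (Table 3) reads "2.5 mg QD: C3D1 onward", again without mention of modified doses.

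**The modification rules.** Section 6.5.1 states: "Dose reductions for individual participants may be made based on events observed at any time during the treatment period". For other clinically significant Grade 3 toxicities, Table 8 says: "If assessed as related to parsaclisib, restart at the next lower dose of parsaclisib (see Table 11". Table 10 also sends several specific toxicities to a lower parsaclisib dose.

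**Table 11** has one dose column for Days 1 to 56 and one for Day 57 to end of treatment. Its three rows are:
- "Starting dose 20 mg QD 2.5 mg QD"
- "First dose reduction 10 mg QD 1 mg QD"
- "Second dose reduction 5 mg QD Not applicable"

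**Table 12** covers diarrhea/colitis. It takes a participant on 2.5 mg QD or more to 20 mg QW, and one on 1 mg QD to 20 or 10 mg QW. From 20 or 10 mg QW the next steps are 10 or 5 mg QW, and from 5 mg QW parsaclisib stops. No row leads back to daily dosing.

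**Section 9.10** defines a parsaclisib overdose after the first 8 weeks as a daily dose above 2.5 mg.

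**The concern.** A participant can reach Day 57 on something other than 20 mg QD, either on a reduced daily dose or on weekly dosing. These participants have, by definition, already had a toxicity that led to a change of dose. For them, Section 6.2.2 gives one instruction, Table 12 gives another, and Table 11 may give a third. No visible sentence says which governs, or whether a modification made before Day 57 carries across the switch.

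The Phase 1b primary objective is safety and tolerability, with the incidence and severity of TEAEs as an endpoint. If investigators resolve the point differently, participants with the same toxicity history will receive different doses from Day 57 until they stop treatment. The question also touches a discontinuation rule. Table 8 stops both drugs when a Grade 3 toxicity recurs after two parsaclisib reductions, whereas Table 11 lists only one reduction step for the period from Day 57. Whether reductions are counted across the switch therefore matters.

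**Working it through.** The question is one of consistency between passages. The only arithmetic is calendar and dose conversion.

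**1. The switch date.** Section 6.2.2 gives 8 weeks of initial dosing: 8 × 7 + 1 = Day 57. Table 11 and the Schedule place the change at Cycle 3 Day 1 with 28-day cycles: 2 × 28 + 1 = Day 57. The date reproduces, so the passages agree on when the switch happens.

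**2. The instruction for each kind of participant on Day 57.**

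| Status just before Day 57 | Section 6.2.2 and Schedule note | Table 11, rows read across | Table 11, columns as separate ladders | Table 12 |
|---|---|---|---|---|
| 20 mg QD | 2.5 mg QD | 2.5 mg QD | 2.5 mg QD | – |
| 10 mg QD | 2.5 mg QD | 1 mg QD | 2.5 mg QD | – |
| 5 mg QD | 2.5 mg QD | no dose listed | 2.5 mg QD | – |
| 20, 10 or 5 mg QW | 2.5 mg QD | not covered | not covered | weekly; further steps only downward |

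**3. Reduced daily dose (Table 11).** Read across, the two instructions for a once-reduced participant differ by 2.5 / 1 = 2.5-fold. In weekly totals this is 2.5 × 7 = 17.5 mg against 1 × 7 = 7 mg. For a twice-reduced participant it is 2.5 mg QD against no listed dose. If each column is its own ladder, Section 6.2.2 and Table 11 agree. The participant reduced early then takes the maintenance dose of the unreduced row, and no visible text says whether that is meant.

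**4. Weekly dosing (Table 12).** This comparison does not depend on how Table 11 is read. At 2.5 mg QD the weekly total is 17.5 mg:
- against 20 mg QW: 17.5 / 20 = 0.875, a lower weekly total;
- against 10 mg QW: 17.5 / 10 = 1.75, a higher weekly total;
- against 5 mg QW: 17.5 / 5 = 3.5, a higher weekly total.

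In all three cases Section 6.2.2 also changes the schedule from weekly back to daily, which Table 12 never does.

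**5. Overdose definition (Section 9.10).** After week 8 the threshold is 2.5 mg in a day. On the dosing day, Table 12's weekly doses are 20, 10 or 5 mg, so 20 / 2.5 = 8, 10 / 2.5 = 4 and 5 / 2.5 = 2 times the threshold. A participant following Table 12 after Day 57 therefore meets the overdose definition at every weekly step, including one who moved to weekly dosing only after the switch.

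**The case against.** **Table 11 need not be read across.** Its columns are headed by period, each has its own starting dose, and the empty second step from Day 57 fits a ladder that runs from 2.5 to 1 mg and ends. This stands. A reader might infer a proven contradiction between Section 6.2.2 and Table 11, but the table contains no carry-across rule, so on that point the documents show only an ambiguity.

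**Section 6.2.2 describes the nominal schedule.** Its sentence concerns delays and interruptions. Section 6.6.2 leaves reductions to clinical judgment in consultation with the medical monitor, and several restarts in Table 10 need that monitor's approval. Section 6.6.2.3 is also permissive about using Table 12. This makes an automatic switch regardless of tolerance less likely in practice. It does not supply a Day 57 rule, and the wording about all participants remains unqualified.

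**The dose may fall anyway.** A reader might infer that reduced participants are returned to a higher dose. They have not previously taken 2.5 mg QD, and the move lowers the daily dose 4-fold from 10 mg (10 / 2.5) or 2-fold from 5 mg (5 / 2.5). Only against 10 and 5 mg QW does the weekly total rise. Reaching those steps before Day 57 takes repeated step-downs within 56 days, and Table 10 stops parsaclisib on some recurrences, so they may be uncommon.

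**The analysis can see what was given.** A reader might infer that safety after Day 57 becomes uninterpretable across sites. The documents do not support that. SAP Section 6.4 summarizes actual dose, average daily dose and modifications, and SAP Appendix A plans separate initial- and maintenance-period exposure tables. The DLT window closes on Day 28, before the switch, and the study is exploratory with no formal tests.

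**Some text is unseen.** The administration cell of Table 6 is blank in the public copy, and the IRT and Pharmacy Manuals are not part of the documents. A carry-over instruction could exist there. The conflict among the visible passages would still need correcting.

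**Conclusion.** The point holds as an internal inconsistency in a dosing instruction. The conflict of Section 6.2.2 and the Schedule note with Table 12 stands on any reading of Table 11: a participant on weekly dosing for diarrhea/colitis is put on a daily schedule on Day 57, at 0.875, 1.75 or 3.5 times the weekly total of 20, 10 or 5 mg QW. The conflict with Table 11 is conditional on reading its rows across, where it amounts to 2.5 mg against 1 mg QD, or 2.5 mg QD against no listed dose. Otherwise it is an unanswered question about intent. The overdose definition is inconsistent with Table 12 after week 8.

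The conclusion rests on the public text and on reading Section 6.2.2 literally. The number of participants affected is not given in the documents and cannot be derived from them; it depends on how many are modified in the first 8 weeks and remain on parsaclisib at Day 57. The matter deserves correction because it concerns participants who have already had toxicity, not because it threatens the analysis. No view is taken on which dose or rule is right.

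**What to change.** The sponsor should reconcile Section 6.2.2, the parsaclisib note in the Schedule of Activities, Table 11 and Table 12. The documents should then give one consistent Day 57 instruction for participants on each reduced daily dose and for those on weekly dosing, and should say whether Table 11's rows or its columns are to be followed across the switch. The overdose definition in Section 9.10 should be reconciled with Table 12's weekly doses at the same time. It would help to state whether reductions before Day 57 count toward the two-reduction rule in Table 8. The choice of dose and rule belongs to the sponsor.

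The cost is a sentence in Section 6.2.2, matching wording in the Schedule note and Section 9.10, footnotes to Tables 11 and 12, and aligned dispensing instructions, carried in a protocol amendment. It adds no participants, visits or procedures, and the planned SAP exposure tables need no new data.

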### **6.3. Measures to Minimize Bias: Randomization and Blinding**

All participants will be centrally assigned to study treatment using an IRT system. Instructions for the IRT system will be provided to each site prior to study initiation. Full details will be provided in the IRT Manual.

Study treatment will be dispensed and administered at the study visits in accordance with the SoA in [Table 3](#). Returned study treatment should not be redispensed.

This is an open-label study; there is no randomization, and no comparisons will be made between participants or against historical controls. Measurements of safety and efficacy are objective measurements, and only comparisons to pretreatment conditions will be made.

### **6.4. Study Treatment Compliance**

Compliance with all study-related treatments should be emphasized to the participant by site personnel, and appropriate steps should be taken to optimize compliance during the study. Compliance with parsaclisib will be calculated by the sponsor based on the drug accountability (eg, tablet counts) documented by the site staff and monitored by the sponsor/designee.

Participants will be instructed to bring all unused study drugs with them to the study visits in order for site personnel to conduct tablet counts to assess study drug accountability.

Compliance with tafasitamab administration will be calculated by the sponsor based on study drug accountability and infusion records documented by the site staff and monitored by the sponsor/designee.

### **6.5. Dose-Limiting Toxicity and Determination of the Recommended Phase 2 Dose**

#### **6.5.1. Definition of a Dose-Limiting Toxicity**

Dose-limiting toxicity will be defined as the occurrence of any of the toxicities in [Table 7](#) up to and including Day 28 (Cycle 1/Day 28), except those with a clear alternative explanation. All DLTs will be assessed for severity by the investigator using CTCAE v5.0 criteria.

During the DLT evaluation period, participants who receive at least 3 of 4 doses of tafasitamab and 21 days of parsaclisib 20 mg QD or have a DLT will be considered evaluable for the dose confirmation period.

Dose reductions for individual participants may be made based on events observed at any time during the treatment period; however, for the purposes of opening each expansion cohort, decisions will be made based on events that are observed from the first day of study treatment administration through and including the final day of Cycle 1 (Cycle 1/Day 28).

An event clearly associated with the underlying disease, disease progression, a concomitant medication, or comorbidity will not be considered a DLT.

**Table 7: Definition of Dose-Limiting Toxicity**

Toxicity	Definition
Nonhematologic	

• Any liver function abnormalities that meet the definition of Hy's lawa.

• <math>\geq</math> Grade 4 tumor lysis syndrome or Grade 3 tumor lysis syndrome requiring dialysis.

• <math>\geq</math> Grade 4 fatigue lasting for <math>\geq</math> 7 days.

• <math>\geq</math> Grade 4 IRR.

• <math>\geq</math> Grade 3 CRS.

• Any other <math>\geq</math> Grade 3 nonhematologic toxicity except nausea, vomiting, electrolyte abnormality, or liver function abnormality

Hematologic	

• <math>\geq</math> Grade 3 hematologic toxicities lasting for <math>> 3</math> days excluding neutropenia and lymphocytopenia (also excluding thrombocytopenia in Groups 3 and 5).

• Grade 4 neutropenia (<math>ANC < 0.5 \times 10^9/L</math>) lasting for <math>\geq</math> 7 days in participants with pretreatment <math>ANC > 1 \times 10^9/L</math> under appropriate use of G-CSF (if G-CSF is required to manage neutropenia, the neutropenia is considered a DLT in Cohorts 1 and 2).

• Grade <math>\geq 4</math> thrombocytopenia in Cohorts 3 and 5.

• Febrile neutropenia.

General	

• Any death not clearly due to the underlying disease or extraneous causes.

• Any toxicity other than described above that (in the opinion of the investigator) is potentially life-threatening and cannot be controlled with standard measures.

• Any other toxicity that a primary investigator and the sponsor agree on being reported as a DLT.

a Hy's law is defined as 1) ALT or AST elevation  $> 3 \times ULN$ , 2) total bilirubin  $> 2 \times ULN$  without initial findings of cholestasis (elevated serum alkaline phosphatase), and 3) no other apparent possible causes of aminotransferase elevation and hyperbilirubinemia, including but not limited to viral hepatitis, pre-existing chronic or acute liver disease, or the administration of other drug(s) known to be hepatotoxic.

